8.3 Analysis of Safety Data

For continuous variables data will be summarized by treatment using n, mean, SD, minimum and maximum values.

For categorical variables data will be summarized by treatment using frequency and percentage.

8.3.1 Adverse Events

Adverse events will be coded using the most recent version of Medical Dictionary for Regulatory Activities (MedDRA). Treatment Emergent AE's (TEAE) are defined as events with an onset on or after the first randomized treatment. TEAEs will be summarized by treatment group, System Organ Class, and preferred term. The following TEAE summaries will be provided:

- Overall (*i.e.*, regardless of severity or relationship to treatment)
- By severity grade (mild, moderate, severe, life threatening or death for SAEs)
- By relationship to clinical trial treatment according to the mapping scheme below:
 - Potentially related: will include all adverse events with a relationship rating of “definitely”, “probably” or “possibly”.
 - Unlikely/not related: will include all adverse events with a relationship rating of “unlikely” or “unrelated”.

Unless otherwise specified, at each level of subject summarization, a subject will be counted only once. If there is more than one occurrence of an event, the event of the worst severity or the worst-case relationship category will be summarized.

In addition, separate summaries of serious adverse events, and adverse events resulting in discontinuation of study treatment will be presented.

AEs leading to premature discontinuation of clinical trial treatment, AEs that lead to study discontinuation, AEs that lead to death and Serious Adverse Events (SAEs) will also be summarized by treatment group and relationship.

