## 5 SUBJECT COMPLETION AND WITHDRAWAL

### 5.1 SUBJECT COMPLETION

A subject who completes TV3 will be considered to have completed the study.

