### 7.1 PROHIBITED MEDICATION

The following treatments and medications are prohibited throughout the study

1. Initiation of any anti-parkinsonian medication (including levodopa, dopamine agonists, entacapone and monoamine oxidase-B inhibitors) for the duration of the trial.
2. Initiation of Amantadine or anticholinergics for newly diagnosed subjects or change in the dosage of Amantadine or anticholinergics during the trial for subjects who were on stable doses for 4 weeks prior to screening.

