### **9.9.3 CONCOMITANT MEDICATIONS/THERAPIES**

Concomitant medications/therapies will be summarized separately for the Safety population. All prior and concomitant medications recorded in the case report form will be coded to all matching Anatomic Therapeutic Classification codes using the most recent version of WHO Drug. Descriptive summaries, by treatment group and stage of the study, will be prepared using the coded term. All concomitant medications/therapies recorded in the case report form will be listed.

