### **9.10.1 ADVERSE EVENTS**

Adverse events will be coded using MedDRA. Treatment Emergent AE's (TEAE) are defined as events with an onset on or after the first randomized treatment. TEAEs will be summarized by treatment group and by stage of the study, System Organ Class, and preferred term. The following TEAE summaries will be provided:

- TEAEs by severity grade
- TEAEs by relationship to study treatment.

In addition, separate summaries of serious adverse events, and adverse events resulting in discontinuation of study treatment will be presented.

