7.3.2 Handling of Missing Data for Safety Evaluations

Adverse Event (AE) Summaries

With respect to summaries of AEs, only AEs that were treatment emergent will be tabulated. Treatment-emergent is defined as AEs with start date \geq date of first treatment administration.

- 1) If AE start date is completely missing, the date of first treatment administration will be taken as the start date of the event.
- 2) If AE start date is partially missing:

- a. If the day part of the start date is missing, the start date will be estimated to be equal to the date of first treatment administration, provided the start month and year are the same as the date of first treatment administration and the stop date either after the date of first treatment administration or completely missing. Otherwise, the AE will be assumed to have started on the first day of the month (01/MMM/YYYY)
- b. If the month part of the start date is missing, the start month will be estimated to be equal to the month of the date of first treatment administration or the following month after the month of the date of first treatment administration depending on the day part of the start date provided that the start year is the same as the year of date of first treatment administration and the stop date is either after date of first treatment administration or completely missing. Otherwise, the AE will be assumed to have started on the first month of the year (DD/Jan/YYYY)
- c. If both the day and month parts of the start date are missing, the start date will be estimated to be equal to the date of first treatment administration, provided the start year is the same as year of date of first treatment administration and the stop date is either after the date of first treatment administration or completely missing. Otherwise, the AE will be assumed to have started on first day and first month of the year (01/Jan/YYYY)
- d. If all day, month and year parts of the start date are missing, the start date will be estimated to be equal to the date of first treatment administration (and thus treatment emergent) provided that the stop date is either after the date of first treatment administration or completely missing. Otherwise, the start date will be estimated to be the first day of the same year as the stop date.

3) If AE stop date is partially or completely missing:

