8.1.2 Major Protocol Deviations

The deviations occurring during the clinical trial will be summarized descriptively according to the following categories:

- Entrance criteria deviation
- Withdrawal criteria deviation
- Received wrong treatment or incorrect dose
- Received an excluded medication
- All other major protocol deviations

Additionally a by-subject listing of all deviations will also be prepared.

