8.1.4 Prior and Concomitant Medications/Therapies

Prior and concomitant medications/therapies will be summarized for the Safety population.

All prior and concomitant medications recorded in the case report form will be coded to all matching Anatomic Therapeutic Classification codes using the most recent version of WHO Drug.

Descriptive summaries, by treatment group, will be prepared using the coded generic term. All prior and concomitant medications recorded in the case report form will be listed.

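### The SAP omits the by-stage split of adverse events and medications that the protocol body calls for, so the four off-drug follow-up weeks are pooled with treatment

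*SAP*

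**What the plan says.** **Adverse events.** Protocol 9.10.1 states: "TEAEs will be summarized by treatment group and by stage of the study, System Organ Class, and preferred term". SAP 8.3.1 states: "TEAEs will be summarized by treatment group, System Organ Class, and preferred term". The Safety Analysis paragraph of the protocol synopsis has the shorter form, as in the SAP.

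**Medications.** Protocol 9.9.3 states: "Descriptive summaries, by treatment group and stage of the study, will be prepared using the coded term". SAP 8.1.4 states: "Descriptive summaries, by treatment group, will be prepared using the coded generic term". The synopsis gives no rule for summarising medications, so 9.9.3 is the protocol's only statement on it.

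**Time window.** Protocol 9.10.1 and SAP 7.3.2 and 8.3.1 count any event that starts on or after the first dose as treatment-emergent. None gives an end. Protocol 10.2 collects events until the final study visit, which Protocol 4.2.1 places at Day 112±3. SAP 2.2 names a 12-week treatment part and a separate 4-week follow-up part, with TV3 as end of treatment.

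**Prohibited drugs and the per-protocol (PP) set.** Protocol 7.1 states: "The following treatments and medications are prohibited throughout the study". The synopsis counts follow-up in its 18-week study duration. Protocol 5.1 states: "A subject who completes TV3 will be considered to have completed the study". SAP 8.1.2, on major deviations, lists "Received an excluded medication" without a time limit. SAP 6.2 excludes from PP anyone with a major violation, also without a time limit, and makes PP the primary efficacy population.

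**The concern.** The primary objective is safety and tolerability of each dose against placebo. With an open-ended definition of treatment-emergence, the split by stage is the only planned device that separates on-drug from off-drug events in the tables. Without it, a reader of those tables cannot tell whether an event began during dosing or in the following four weeks. Each subject is counted once, at worst severity or closest relationship, which hides timing further. The share of off-drug time is largest for subjects who stop early, and they matter most for tolerability.

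The same lack of a boundary at TV3 touches efficacy. No motor score is taken after TV3. If a Parkinson's drug started during follow-up were handled as a major violation, a Week 12 score that it could not have influenced might leave the primary analysis.

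**Working it through.** **1. The plan's own figures.** Study duration: 2 + 12 + 4 = 18 weeks, as the synopsis states, so the protocol counts follow-up as part of the study. Sample size: 3 × 20 = 60, as stated.

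**2. Off-drug share of the window.** Inputs: TV3 at Day 84±3 (Protocol 4.1.3) and follow-up at Day 112±3 (Protocol 4.2.1). Share = (follow-up day − TV3 day) / follow-up day, taking TV3 as the end of dosing.

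- Nominal: (112 − 84)/112 = 28/112 = 25%.
- Shortest: (109 − 87)/109 = 20.2%.
- Longest: (115 − 81)/115 = 29.6%.
- Withdrawn at Week 4, with follow-up 4 weeks after the end-of-study evaluations (Protocol 5.2): 4/(4 + 4) = 50%.

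**3. Possible dilution (illustration).** The documents give no event rates. Assume a constant weekly rate h on placebo, doubled on active while dosing and equal to placebo afterwards.

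- Rate ratio: 2.0 on treatment; pooled (12×2 + 4×1)/16 = 28/16 = 1.75.
- Proportion with an event, at h = 0.04:

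| Window | Placebo | Active | Difference | Risk ratio |
|---|---|---|---|---|
| 12 weeks | 1 − exp(−0.48) = 38.1% | 1 − exp(−0.96) = 61.7% | 23.6 points | 1.62 |
| 16 weeks | 1 − exp(−0.64) = 47.3% | 1 − exp(−1.12) = 67.4% | 20.1 points | 1.43 |

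- Over h = 0.01 to 0.10, the risk ratio falls from 1.89 to 1.65 at the lowest rate and from 1.30 to 1.18 at the highest.
- For scale: 23.6 − 20.1 = 3.5 points, or 0.035 × 20 = 0.7 of a subject per arm. The standard error of the 12-week difference is √[(0.381×0.619 + 0.617×0.383)/20] ≈ 15 points.

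**4. PP consequence (illustration).** The documents give no SD, effect or rate of drug starts. If 10% to 40% of each arm left PP only because of a drug started after TV3, n per arm would fall from 20 to between 18 and 12. The difference detectable with 80% power at two-sided 0.05, (1.96 + 0.84) × √(2/n), would rise from 0.89 SD to between 0.93 and 1.14 SD. If starting is unrelated to change, the expected PP difference does not move. If subjects who worsened start more often, it can. Assume SD 8, a true effect of −5 and a placebo mean change of +1, with 10% of other subjects starting. With 30% (60%) of those who worsened by 5 or more also starting, the PP difference becomes −4.7 (−4.1).

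**The case against.** The strongest reply is that little is lost. Protocol 10.2 records onset and end dates for every event, and Protocol 10.2.1 has a code for events after the treatment phase. All data are listed, and events leading to discontinuation of treatment are tabulated separately. Safety is descriptive, and the illustrated shift is under one subject per arm. This stands: the data exist, and what is missing is a table layout. It does not explain why the SAP omits a layout that the protocol body asks for.

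The SAP's sentence also matches the synopsis, and the open-ended definition comes from the protocol. That stands for adverse events, where the SAP follows one of two conflicting protocol statements. It does not cover medications.

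Dilution towards placebo is not certain. This is the first human study, so delayed or withdrawal effects cannot be ruled out, and with these pooling need not bring the arms together. A split by part would help in that case too.

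Two stronger readings are tempting. A reader might infer that the SAP treats follow-up as treatment; SAP 2.2 names it as a separate part and ends treatment at TV3. A reader might also infer that a drug started in Week 13 does remove the subject from PP. No document says so. SAP 8.1.2 only summarises deviations descriptively, SAP 6.2 fixes PP before lock and unblinding, Protocol 5.1 points the other way, and the supportive ITT analysis does not exclude subjects for such a deviation.

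**Conclusion.** The point holds as an omission in the SAP and an inconsistency within the protocol. About a quarter of a completer's treatment-emergent window, and about half for a subject withdrawn at Week 4, is off drug and is not separated in any planned summary. Those shares follow from the visit schedule, taking dosing to end at TV3 or at the withdrawal visit. The fall in rate ratio from 2.0 to 1.75 depends on assumed rates and on drug effects ending with dosing. Its effect on counts is small against the sampling error at 20 per arm.

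The PP matter is secondary and conditional. The untimed wording of SAP 6.2, read with Protocol 7.1 and the 18-week duration, permits removal for an event after the outcome was measured, but does not require it. The PP figures above only illustrate what could follow.

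**What to change.** 1. In SAP 8.3.1 and 8.1.4, restore the split: present treatment-emergent events and medications by double-blind treatment part and follow-up part, keeping the all-events table alongside. State one cut-off date. Last dose and the TV3 or early-termination visit can differ for anyone who stops dosing before the visit, so the SAP should name one of them; Protocol 6.9 has subjects report the time of their last dose.
2. Reconcile the synopsis sentence on adverse events with Protocol 9.10.1.
3. In SAP 6.2, state before unblinding that a deviation dated after the subject's Week 12 efficacy assessment does not by itself remove that subject from the PP analysis. This concerns the analysis set only.
4. The sponsor should reconcile Protocol 7.1 and the 18-week duration with Protocol 5.1. No clinical rule is proposed here.

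The cost is a few sentences and one extra set of tables. An event that begins just after the cut-off will appear under follow-up, but it remains in the all-events table.

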8.3.2 Columbia-Suicide Severity Rating Scale (C-SSRS)

All the data from C-SSRS will be listed and descriptive summaries will be presented for each of the subscales (i.e. Suicidal Ideation and Suicidal Behavior).

8.3.3 Clinical Laboratory Evaluations

The laboratory assessments in this study include Biochemistry, Hematology and Urine analysis. All available data will be summarized or presented as a by-subject listing as follows:

8.3.3.1 Laboratory Values over Time

Summary statistics of raw data and change from baseline values for each laboratory parameter will be presented by treatment group and time point. Data will be summarized as appropriate for the variable type.

- For continuous data, summaries will include the number of observations, mean, SD, median, minimum, and maximum values.
- For categorical data, frequency counts and percentages will be used.

For change from baseline summaries, subjects with an undefined change from baseline, because of missing data, will be excluded.

8.3.3.2 Individual Subject Changes (Shift Tables)

Individual subject changes will be identified through shift tables. Shift tables will be presented for each laboratory parameter with counts and percentages of subjects, by treatment group and time point, for shift (change) from baseline, using the normal ranges from the laboratory.

8.3.3.3 Individual Clinically Significant Abnormalities

Clinically significant laboratory abnormalities (i.e., those laboratory abnormalities recorded as AEs) will be listed.

All results of laboratory evaluations will be presented as by-subject listings

8.3.4 Vital Signs and Weight

Tabulations of raw data and change from baseline values will be presented by time point for each vital sign parameter and weight.

Tabulations will include the number of observations, mean, standard deviation, median, and minimum and maximum values. For change from baseline summaries, subjects with an undefined change from baseline, because of missing data, will be excluded.

8.3.5 ECG

All ECG findings will be listed and/or summarized. Shift tables will also be presented to show any abnormality shifts from baseline to post baseline visits.

8.3.6 Physical Examination

All physical examination findings will be listed and/or summarized by treatment group. Shift tables will also be presented to show any abnormality shifts from baseline to post baseline visits.

9. APPENDIX 1: SCHEDULE OF ASSESSMENTS

Study Parts	Screening Part (2 weeks)	Double-Blind Treatment Part (12 weeks)				Follow-up Part Follow-up visit (4 weeks)			
		TV0 Randomization		TV1	TV2				
Treatment Visits		Day 0				FUV			
Weeks from Randomization Date (window period: \pm days)	- 2			+ 4 (\pm 3)	+ 8 (\pm 3)	+ 12 (\pm 3)			
		Pre-							
		Post-							
Written Informed Consent	X								
Inclusion/Exclusion Criteria	X								
Schedule Randomization Day	X								
Continued Eligibility		X							
Randomization		X							
Demographics	X								
Medical History	X	X							
Physical Examination	X	X		X	X	X			
Vital Signs	X	X	X	X	X	X			
Height ¹ and Weight	X	X				X			
ECG	X	X		X		X			
Serum Hematology ²	X			X	X	X			
Serum Chemistry ²	X			X	X	X			
Urine Analysis ²	X			X	X	X			
Urine Pregnancy Test ³	X	X				X			
MDS-UPDRS		X		X	X	X			
H & Y	X	X		X	X	X			
S & E		X		X	X	X			
PDQ-39		X		X	X	X			
CGI-S and CGI-I ⁴	X	X		X	X	X			
C-SSRS	X	X		X	X	X			
MMSE	X	X							
Dispense the DA-9805 or placebo ⁵			X	X	X				
DA-9805 or Placebo first dose administration			X						
Study treatment accountability				X	X	X			
Adverse Events			X	X	X	X			
Concomitant medications	X	X		X	X	X			

¹ Height only at Screening.

² Subjects who meet eligibility criteria, but have some abnormal laboratory values, based on PI review a repeat laboratory sample may be collected. The repeat laboratory reports should be reviewed by the PI to confirm eligibility prior to randomization.

³ Only for female subjects of childbearing potential.

⁴ CGI-I will be done only at Treatment Visit 1 to Treatment Visit 3

⁵ Dispense the DA-9805 or placebo at each of the clinic treatment visit, except TV3 which is the End of Treatment visit (EOT).

10. APPENDIX 2 – PLANNED TLG

10.1 Planned by-subject listings

DISPOSITION/WITHDRAWALS (LISTINGS 16.2.1.X)

ELIGIBILITY AND PROTOCOL DEVIATIONS (LISTINGS 16.2.2.X)

EXCLUDED SUBJECTS (LISTINGS 16.2.3.X)

DEMOGRAPHICS, POPULATION, AND BASELINE CHARACTERISTICS
(LISTINGS 16.2.4.X)

DRUG COMPLIANCE AND DRUG CONCENTRATION LISTINGS (LISTINGS
16.2.5.X)

EFFICACY RESPONSE (LISTINGS 16.2.6.X)

ADVERSE EVENT DATA (LISTINGS 16.2.7.X)

SAFETY DATA (LISTINGS 16.2.8.1.X)

10.2 Planned Summary Tables

POPULATION DISPOSITION AND PROTOCOL DEVIATIONS
POPULATION DEMOGRAPHICS AND BASELINE CHARACTERISTICS
CONCOMITANT MEDICATION USAGE
EFFICACY SUMMARIES
SAFETY SUMMARIES
 ADVERSE EVENT SUMMARIES
 SERIOUS ADVERSE EVENTS
 LABORATORY
 VITAL SIGNS AND PHYSICAL EXAMINATION (PE)
 COLUMBIA-SUICIDE SEVERITY RATING SCALE (C-SSRS)
 OTHER SAFETY

11. VERSION HISTORY

This is the first version.

